## 7.4. Agent Administration

The investigator will instruct the patient to take the study drugs exactly as specified in the protocol. A pill diary will be given to all patients enrolled in the study. A cycle will last 28 days.

	1 cycle = 28 days				
N of pts.  Dose Level (IV q15 days)  Cobimetinib Idasanutlin (PO daily x 21 out of 28 days)  Cobimetinib Idasanutlin (PO daily x 5 out 28 days)		(PO daily x 5 out of			
			Phase Ib		
3-6	3	840 mg		200 mg	
3-6	2	840 mg		150 mg	
3-6	1	840 mg		100 mg	
3-6	–1	840 mg		50 mg	
	Phase II				
40		840 mg	60 mg		
40		840 mg		TBD	

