# 7.5. Definition of Dose-Limiting Toxicity (DLT) – for patients on idasanutlin armonly

Any of the following events that occur during cycle 1 (first 6 weeks) will be considered a DLT when classified as possibly, probably or definitively related to study treatment (according to NCI CTEP Adverse Event Reporting Requirements). Apart from the criteria listed below, if a lower grade AE leads to a dose interruption of more than 14 consecutive days of study drugs for the first 4 weeks of Cycle 1, this AE will be considered a DLT; patients must receive at least 75% of study drug during cycle 1 in order to be evaluable for the DLT observation period. Whenever a patient experiences toxicity that fulfills the criteria for a DLT, treatment with the study drug responsible for the toxicity will be interrupted (patient may continue the remainder study drugs) and the toxicity will be followed up. The Protocol Chair must be notified immediately of any DLT:

TOXICITY	DLT CRITERIA			
	Anemia CTCAE Grade ≥ 3 > 14 consecutive days			
	Febrile neutropenia CTCAE Grade ≥ 3			
5	ANC CTCAE Grade 3 for > 14 consecutive days			
Blood and lymphatic system disorders	ANC CTCAE Grade 4			
system disorders	Platelet count CTCAE Grade 3 for > 7 consecutive days and/or with signs of bleeding			
	Platelet count CTCAE Grade 4			
Ocular diserders	CTCAE Grade ≥ 2 for > 14 days			
Ocular disorders	CTCAE Grade ≥ 3			
General disorders and administration site conditions	Fatigue CTCAE Grade 3 for > 14 consecutive days			
Skin and subcutaneous tissue disorders	Skin, mucosal or nail toxicity CTCAE Grade ≥ 3 for > 14 consecutive days despite treatment			
GI disorders a	Diarrhea CTCAE Grade ≥ 3 for ≥ 48 hrs, despite the use of anti- diarrhea therapy			
Gi disorders*	Nausea/vomiting CTCAE Grade ≥ 3 for ≥ 48 hrs, despite the use of anti-emetic therapy			

TOXICITY	DLT CRITERIA			
	Constipation CTCAE Grade ≥ 3 for ≥ 48 hrs, despite the use of anti-constipation therapy			
	Blood bilirubin c CTCAE Grade 2 for > 7 consecutive days			
	Blood bilirubin c CTCAE Grade ≥ 3			
Investigations b	AST or ALT CTCAE Grade ≥ 3 in conjunction with blood bilirubin c CTCAE Grade ≥ 2 of any duration			
	AST or ALT CTCAE Grade 3 for > 7 consecutive days			
	AST or ALT CTCAE Grade 4			
	Alkaline phosphatase CTCAE Grade 4			
	Any other CTCAE ≥ Grade 3 toxicity except for:			

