# 7.6. Definition of Maximum Tolerated Dose (MTD) – for patients on idasanutlin arm only

The MTD will be defined as the highest dose tested in which a DLT is experienced by 0 out of 3 or 1 out of 6 patients among the dose levels. The first cohort of patients (3 patients) will be started at dose level 1, and each patient will be observed for 6 weeks on the specified dose:

If no patient in the first cohort of 3 experiences a DLT, accrual will continue to test the next dose level
If 1 patient experiences a DLT any given cohort/ dose level, an additional cohort of 3 patients will be treated at the same dose level
If 1 patient has a DLT out of 6 patients treated at this same dose, accrual will continue to test the next dose level
If 2 or more patients in 3 or 6 patients treated at a given dose experience DLT, the dose will be de-escalated to the next lower dose level. If the current dose level is at -1, the regimen will be considered too toxic and the corresponding cohort within the study will be discontinued
If 0 out of 3 or 1 out of 6 patients has a DLT treated at dose level 3, accrual will continue to the phase II portion of the study

No new cohort of patients will be treated until the previous cohort has been fully evaluated for toxicity and a dose escalation decision has been made. Routine updates regarding patient and study status will be conducted.

Once the MTD is reached, the expansion component of the study will be completed to assess tolerability and efficacy. Patients in the phase II portion of the study will initiate study treatment at the MTD defined in the escalation component of the trial. Note that dose reduction within patients (individually) is allowed after the 4 week DLT observation period in the escalation and in the expansion components of the study (see Dose Modification guidelines, Section 8). Intrapatient dose escalation will not be allowed. Dose reduction will be required for a given patient in case of:

- ☐ Grade 3 or 4 toxicities
- Grade ≥ 2 elevation of creatinine, bilirubin, AST, or ALT lasting more than 14 days despite medical treatment, or
- Grade ≥ 2 ocular, skin or nail toxicity for more than 28 days in a row despite optimal medical treatment, or
- Grade ≥ 2 GI toxicity lasting more than 14 days despite medical treatment.

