## Management of Symptomatic LVEF Decrease from Baseline:

- Consider holding atezolizumab; discuss with Medical Monitor regarding resumption of atezolizumab
- Cardiology consultation strongly recommended
- Withhold cobimetinib dosing for at least 4 weeks for symptomatic LVEF decrease.
- Permanently discontinue cobimetinib if after 4 weeks patient continues to have symptomatic heart failure despite maximal supportive care or if LVEF has not recovered to ≥ 40% or to < 10% absolute decrease below pretreatment values.
- If heart failure symptoms have resolved following treatment break and LVEF has recovered to  $\geq$  40% or to < 10% absolute decrease below pretreatment values, resume cobimetinib at:
  - 1st dose level down for first appearance of LVEF decline
  - 2nd dose level down for second appearance of LVEF decline
  - Permanently discontinue cobimetinib for a third episode of LVEF decline

Hematology (Cobimetinib or Idasanutlin)			
ANC decreased (Neutropenia)			
Grade 1 / 2	Maintain dose level of Cobimetinib or Idasanutlin.		
	Omit dose of Cobimetinib or Idasanutlin until ANC ≥ 1000/mm³, then		
Grade 3	- If resolved in ≤ 7 days, then maintain dose level of Cobimetinib or Idasanutlin.		
	- If resolved in > 7 days, then ↓ 1 dose level of Cobimetinib or Idasanutlin.		
Grade 4	Omit dose of Cobimetinib until ANC ≥ 1000/mm³, then ↓ 1 dose level of Cobimetinib or		
Grade 4	Idasanutlin.		

Protocol Chair: [name]

Anemia							
Grade 1 / 2	Maintain dose level of Cobimetinib or Idasanutlin.						
Grade 3	Omit dose of Cobimetinib or Idasanutlin until resolved to CTCAE Grade ≤ 1 or baseli						
Grade 4 Discontinue Cobimetinib or Idasanutlin.							
Febrile neutrope	Febrile neutropenia						
	Omit dose of Cobimetinib or Idasanutlin, then						
Grade 3	- If resolved by ≤ 7 days, then, ↓ 1 dose level of Cobimetinib or Idasanutlin.						
	- If not resolved within 7 days discontinue Cobimetinib or Idasanutlin.						
Grade 4	Discontinue Cobimetinib or Idasanutlin.						
Platelet count de	ecreased (Thrombocytopenia)						
Grade 1 / 2	Maintain dose level of Cobimetinib or Idasanutlin.						
	Omit dose of Cobimetinib or Idasanutlin until resolved to CTCAE Grade ≤ 1, then						
Grade 3	- If resolved in ≤ 7 days, then ↓ 1 dose level of Cobimetinib or Idasanutlin.						
Oldde o	- If resolved in > 7 days and/or with signs of bleeding, then discontinue patient from						
	Cobimetinib or Idasanutlin.  Discontinue Cobimetinib or Idasanutlin.						

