#### Phase Ib Trial of Idasanutlin and Atezolizumab 24.1.

For the dose-escalation study, a standard 3 + 3 dose escalation scheme will be utilized to evaluate the primary objective of determining a RP2D (Recommended Phase II Dose) for Idasanutlin in combination with Atezolizumab. Three dosing cohorts of Idasanutlin will be evaluated in combination with Atezolizumab (dosage will be held constant at 840 mg) to determine the RP2D and will occur in accordance with the dose escalation rule below.

1 Cycle = 28 days			
N of pts.	Dose Level	Atezolizumab (IV q15 days)	Idasanutlin (PO daily x 5 out of 28 days)
3-6	3	840 mg	200 mg
3-6	2	840 mg	150 mg
3-6	1	840 mg	100 mg
3-6	-1	840 mg	50 mg

DLTs are defined in section 7.5 and will be assessed during a DLT assessment window, which is during the first cycle of therapy. The RP2D from this study will be utilized in the Idasanutlin +

Atezolizumab arm in the Phase II portion of this study. The determination of the MTD and RP2D are reviewed in the following table. Of note, the PI may adjust the RP2D based on overall tolerability after cycle 1 at their discretion after discussion with all study Pl's.

Number of Patients with DLT at a given dose level	Escalation Decision Rule
0 out of 3	Enter 3 patients at the next dose level.  If dose level 3 is reached without DLT, then dose level 3 will be considered the MTD and RP2D.
>= 2	Dose escalation will be stopped. This dose level will be declared the maximally administered dose (highest dose administered), exceeding the MTD. Three (3) additional patients will be entered at the next lowest dose level if only 3 patients were treated previously at that dose.
	If this occurs at dose level 1, then 3-6 additional patients will be enrolled on dose level -1, based on toxicity occurring at that dose level. If ≥ 2 patients experience DLT at dose level -1, then the study is considered a failure.
1 out of 3	Enter at least 3 more patients at this dose level. If 0 of these 3 patients experience DLT, proceed to the next dose level. In the event that enrollment is on dose level 3 when this occurs, then dose level 3 is considered the MTD and the RP2D.
1 out of 3	If 1 or more of this group suffer DLT, then dose escalation is stopped, and this dose is declared the maximally administered dose. Three (3) additional patients will be entered at the next lowest dose level if only 3 patients were treated previously at that dose.

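### The Grade 4 neutrophil row in Section 8.5 names only cobimetinib in its hold, so the idasanutlin hold is implied but not written

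*Combined protocol and SAP*

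**What the plan says.** The block in Section 8.5 opens with "Hematology (Cobimetinib or Idasanutlin", so its rows apply to both oral drugs. For Grade 3 neutropenia the instruction is "Omit dose of Cobimetinib or Idasanutlin until ANC ≥ 1000/mm³", followed by the same dose or one level lower, depending on how fast the count recovers. For Grade 4 the row reads "Omit dose of Cobimetinib until ANC ≥ 1000/mm³, then ↓ 1 dose level of Cobimetinib or", and its last word is idasanutlin.

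Four other places bear on the same event in the idasanutlin arm:

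- Section 7.5 lists Grade 4 ANC as a DLT criterion. The window is set by "Any of the following events that occur during cycle 1 (first 6 weeks) will be considered a DLT", and for toxicity meeting the criteria "treatment with the study drug responsible for the toxicity will be interrupted".
- The follow-up table in Section 7.5 ties re-treatment after Grade 3 or worse neutropenia to recovery to Grade 1 or better.
- Section 7.6 requires a dose reduction after Grade 3 or 4 toxicity.
- The idasanutlin rules in Section 8.5 base each modification on the worst toxicity that came before it.

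**The concern.** The two arms are exclusive. Under Section 7.3, TP53-mutated patients receive cobimetinib and TP53 wild-type patients receive idasanutlin. A hold that names only cobimetinib therefore gives idasanutlin-arm patients no explicit instruction to stop. Taken literally, they are held at Grade 3, while at Grade 4 they are only reduced.

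The event is a plausible one. Section 8.3.1 lists neutropenia and febrile neutropenia as anticipated idasanutlin toxicities, and Section 8.3.2.2 describes exposure-dependent marrow suppression with a raised infection risk. Timing makes the hold the instruction that matters. Routine counts fall on Day 1 of each cycle (Synopsis, Safety Assessment; Section 6), which is the day the five-day idasanutlin course begins (Section 7.4.3). The extra mid-cycle counts are for phase Ib only (Section 6, note 12). A Grade 4 count can thus be read just when the site must decide whether to dose.

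**Working it through.** **Step 1: compare the holds in the Hematology block.**

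| Row | Drugs named in the hold |
|---|---|
| ANC, Grade 3 | cobimetinib or idasanutlin |
| ANC, Grade 4 | cobimetinib only |
| Anemia, Grade 3 | cobimetinib or idasanutlin |
| Febrile neutropenia, Grade 3 | cobimetinib or idasanutlin |
| Platelets, Grade 3 | cobimetinib or idasanutlin |

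Five rows contain a hold. Four name both drugs and one does not. The Grade 4 rows for anemia, febrile neutropenia and platelets stop either drug outright, so they need no hold.

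**Step 2: can the Grade 3 hold stand in?** No. Section 8.5 keys modifications to the worst preceding toxicity, so a Grade 4 count is governed by the Grade 4 row.

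**Step 3: look for the hold elsewhere.**

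| Place | What it gives | Plainly orders the hold after the DLT window? |
|---|---|---|
| 7.5, DLT rule | interrupts the responsible drug when DLT criteria are met | not plainly; clear only inside the window |
| 7.5, follow-up table | weekly counts; re-treatment only at Grade 1 or better | no; its lead-in addresses patients already interrupted |
| 7.6 | dose reduction for Grade 3 or 4 | no |
| 8.3.2.2 | monitoring, transfusion and growth-factor advice | no |
| 8.5, Other AEs, Grade 4 | discontinuation | no; ANC has its own row |
| 8.6 | investigator discretion to reduce | no |

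**Step 4: when does the window close?** The documents give it in three ways: six weeks (Section 7.5, above); four weeks, in "dose reduction within patients (individually) is allowed after the 4 week DLT observation period" (Section 7.6); and the first cycle, in "will be assessed during a DLT assessment window, which is during the first cycle of therapy" (Section 24.1). On cycle length, Section 7.4 says "A cycle will last 28 days".

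- Cycle 2 Day 1 = 28 + 1 = day 29. Cycle 3 Day 1 = 2 × 28 + 1 = day 57.
- A six-week window ends on day 6 × 7 = 42. A four-week or first-cycle window ends on day 28.
- Day 29 is inside the six-week window and outside the other two. Day 57 is outside all three.

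So the explicit DLT interruption has clearly lapsed by Cycle 3 Day 1 at the latest, and by Cycle 2 Day 1 on the shorter readings.

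**Step 5: compare the restart levels.** Section 8.5 uses 1000/mm³; the follow-up table in Section 7.5 uses Grade 1 or better. The documents do not reproduce the CTCAE cut points. However, the ANC rows keep the dose unchanged at Grade 1 or 2 and lift the Grade 3 hold at 1000/mm³. That layout indicates that 1000/mm³ marks a return to Grade 2, not to Grade 1.

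**Step 6: background frequency (Section 3.7.2.4).** No Grade 4 rate is given. In Study NP27872, Grade 3 or worse neutropenia was reported in 16 of 99 patients and neutrophil count decrease in 5 of 99. That is 16/99 = 16.2% if the two terms fully overlap and (16 + 5)/99 = 21.2% if they do not. In Study NP28902 it was 3/61 = 4.9%. These figures cap the Grade 4 share in those studies. Doses and schedules differed, so they are context and not a forecast.

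**The case against.** The strongest reply is that the protocol, read as a whole, already leads to a hold.

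- The row makes the lower idasanutlin dose follow recovery to 1000/mm³, and Section 7.6 rules out the full dose after Grade 4 toxicity once the observation period is over. The only course that satisfies both is to wait.
- The hematology row of the Section 7.5 follow-up table is triggered by Grade 3 or worse neutropenia. It sits in a section headed for the idasanutlin arm and is not expressly limited to cycle 1.
- The DLT interruption sentence turns on meeting the criteria, and can be read without a time limit.
- Exposure is narrow. Idasanutlin is taken on 5 of 28 days, so a hold matters only when Grade 4 neutropenia is present at or during a course. Growth-factor support is allowed (Section 7.7).

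Most of this stands, and it lowers the severity. It rules out a stronger inference that a reader might draw: that idasanutlin-arm patients may keep dosing through Grade 4 neutropenia, or that they have no restart threshold. The row's order of steps contradicts the first, and both the row and the follow-up table supply a threshold.

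What does not stand is that the hold is already written. It has to be assembled from two sections, or inferred from a table whose lead-in presupposes an interruption, or from a DLT rule whose window is worded three ways. A site that leaves the row to find the missing rule also meets a different restart level.

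**Conclusion.** The point holds as a drafting slip of low severity in an operative safety rule. One of five hematology holds omits idasanutlin, and it is the one for the more severe neutrophil grade. The intended action is clear and most sites would probably hold. Still, after the DLT window no passage plainly orders it, and two restart conditions are in print.

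This rests on two assumptions. The first is that the omission is in the protocol table itself; the row reads continuously and only its last word wraps to a new line, so a conversion fault looks unlikely. The second is that the DLT interruption is confined to its window; on the unlimited reading the gap is smaller still.

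A reader might also infer dosing gaps from the Grade 3 colitis restart and the Grade 3 row under Other AEs, which name only cobimetinib for the reduced dose. The documents do not support that: Section 7.6 requires the reduction and the idasanutlin table in Section 8.5 defines the next level. No endpoint, sample size, power or type I error figure is affected.

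**What to change.** 1. In the Grade 4 ANC row, add idasanutlin to the hold so that it opens as the Grade 3 row does: "Omit dose of Cobimetinib or Idasanutlin until ANC ≥ 1000/mm³". Leave the one-level reduction for either drug as it stands.
2. Choose one restart level for idasanutlin, either 1000/mm³ or Grade 1 or better, and state it in both Section 8.5 and the Section 7.5 follow-up table. The follow-up table is triggered from Grade 3, so the choice should cover the Grade 3 and Grade 4 rows alike.
3. Optionally, name idasanutlin in the Grade 3 colitis restart and in the Grade 3 reduction under Other AEs, for consistency only.

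The first item costs two words. The second needs a clinical decision by the Protocol Chair and a short edit in one of the two sections. All three can go into the next amendment. The cobimetinib rule for neutropenia, the endpoints, the sample size and the analysis stay as they are.

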For any treatment emergent onset of Grade ≥ 2 visual symptoms or ocular toxicity, Cobimetinib must be interrupted pending diagnostic evaluation, which will include a complete ophthalmologic examination. If RVO is diagnosed, Cobimetinib dosing should be permanently discontinued and the RVO treated per institutional guidelines.

General considerations: Avoid unnecessary	exposure to sunlight,	use sunglasses	in bright
light.		_	

□ Prophylactic management: Frequent use of artificial tear substitutes is strongly recommended.

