General guidance	
 
An ophthalmologist should evaluate visual complaints.
 
Uveitis or episcleritis and other immune–mediated ocular disease may be associated with atezolizumab and may be treated with topical corticosteroid eye drops. Atezolizumab should be permanently discontinued for immune-related ocular event that is unresponsive to local immunosuppressive therapy.
 
Serous retinopathy is associated with cobimetinib. In clinical trials, most events were Grade 1 (asymptomatic) or 2 (symptomatic). Most events in clinical trials resolved or improved to asymptomatic grade 1 following dose interruption or reduction. If serous retinopathy is diagnosed, cobimetinib should be withheld until visual symptoms improve to Grade ≤1. Serous retinopathy can be managed with treatment interruption, dose reduction or with treatment discontinuation.
 
Retinal vein occlusion (RVO) has been reported in patients treated with MEK inhibitors other than cobimetinib.
 
				
Serous retinopathy  Severity grade assessment based on NCI CTCAE v4 "Eye Disorders – Other" scale	Serous retinopathy, Grade 1 or 2 (tolerable):  • Continue cobimetinib and atezolizumab without dose change.  • Continue ophthalmology follow-up as clinically indicated.				

	Serous retinopathy, Grade 2 (intolerable) or 3/4:				
	
 
Interrupt cobimetinib until grade ≤1.
 
				
	Continue atezolizumab as clinically indicated.				
	Consult ophthalmology and undergo complete ophthalmologic examination, which				
	includes visual acuity testing, intra-ocular pressure measurements, slit lamp				
	ophthalmoscopy, indirect ophthalmoscopy, visual field, and OCT. Consider a				
	fluorescein angiogram and/or indocyanine green angiogram, if clinically indicated.				
	
 
Cobimetinib should be dose reduced by 1 dose level when restarting.
 
				
	Consider permanent discontinuation of cobimetinib if serous retinopathy recurs				
	despite 2 dose level reductions				
Retinal vein	If RVO (any grade) is diagnosed, cobimetinib dosing should be permanently				
occlusion (any	discontinued and RVO treated per institutional guidelines.				
grade)	Continue atezolizumab.				
	Grade 1: continue atezolizumab (if symptoms persist, treat as grade 2)				
Potential immune-	Grade 2:				
related ocular toxicity	hold atezolizumab				
(e.g., uveitis, iritis,	
 
resume atezolizumab if event resolves to grade 1 or better within 12 weeks
 
				

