## 15. ADVERSE EVENT REPORTING REQUIREMENTS

#### 15.1. General

Adverse event collection and reporting is a routine part of every clinical trial. This study will use the descriptions and grading scales found in the NCI Common Terminology Criteria for Adverse Events version 5.0 (CTCAE v5.0) that is available at http://ctep.cancer.gov/reporting//ctc.html.

Information on all adverse events, whether reported by the participant, directly observed, or detected by physical examination, laboratory test or other means, will be collected, recorded, followed and reported as described in the following sections.

Adverse events experienced by participants will be collected and reported from initiation of study medication, throughout the study, and within 28 days (+/- 7 days) of the last dose of study medication. Participants who experience an ongoing adverse event related to a study procedure and/or study medication beyond 28 days (+/- 7 days) will continue to be contacted by a member of the study team weekly until the event is resolved, stabilized, or determined to be irreversible by the participating investigator.

Participants should be instructed to report any serious post-study event(s) that might reasonably be related to participation in this study. The investigator should notify the IRB (as per institutional guidelines) and any other applicable regulatory agency of any unanticipated death or adverse event occurring after a participant has discontinued or terminated study participation that may reasonably be related to the study drugs.

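### The Section 8.5 ocular table gives two different cobimetinib instructions for diagnosed, tolerable Grade 2 serous retinopathy

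*Combined protocol and SAP*

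**What the plan says.** Three places in the protocol direct cobimetinib dosing when serous retinopathy is suspected or found.

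- **Section 8.5, ocular table, general guidance.** "If serous retinopathy is diagnosed, cobimetinib should be withheld until visual symptoms improve to Grade ≤1". The same cell describes Grade 1 as asymptomatic and Grade 2 as symptomatic, and adds: "Serous retinopathy can be managed with treatment interruption, dose reduction or with treatment discontinuation". Continuing unchanged is not among the options it lists.
- **Section 8.5, ocular table, serous retinopathy rows.** For Grade 1 or tolerable Grade 2: "Continue cobimetinib and atezolizumab without dose change", with ophthalmology follow-up as clinically indicated. Interruption until Grade 1 or lower is assigned to intolerable Grade 2 and to Grade 3 or 4.
- **Section 8.2.1.5, Visual Disturbances.** "For any treatment emergent onset of Grade ≥ 2 visual symptoms or ocular toxicity, Cobimetinib must be interrupted pending diagnostic evaluation". The evaluation includes a complete eye examination. This sentence does not separate tolerable from intolerable symptoms.

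The label of the serous retinopathy row says "Severity grade assessment based on NCI CTCAE v4". Section 15.1 sets the "Common Terminology Criteria for Adverse Events version 5.0" for the trial, and the synopsis (Study Assessments) and the severity subsection of Section 17.2.2 also name v5.0.

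**The concern.** The general guidance and the row below it address the same decision: what happens to cobimetinib once serous retinopathy has been diagnosed. For one group, symptomatic patients who tolerate their symptoms, they give different answers. The protocol does not define tolerable, and it does not say that a grade-specific row overrides general guidance.

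Sections 8.2.1.5 and 8.5 both identify serous retinopathy as a cobimetinib risk. Section 8.2.1.5 notes that some patients had a recurrence of retinal detachment on re-challenge. The calendar in Section 6 schedules eye examinations at baseline, at Cycle 2 Day 1 and every 12 weeks in the cobimetinib arm, so cases are likely to be looked for and found. Two sites could each follow a line of the protocol and treat the same patient differently. Retinal safety management would then depend on which line was read. So would cobimetinib exposure and the record of interruptions behind the adverse event profile, which is a secondary endpoint.

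**Working it through.** The plan gives no figure of its own on this point, so there is none to reproduce. The check is a comparison of the text by category, followed by an estimate of how many patients could be affected.

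**Step 1. Diagnosed serous retinopathy in the Section 8.5 table**

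| Category | General guidance | Serous retinopathy rows | Result |
|---|---|---|---|
| Grade 1 (asymptomatic) | The condition for ending the hold is already met | Continue unchanged | No clear conflict |
| Grade 2, tolerable | Withhold until Grade 1 or lower | Continue unchanged | Direct conflict |
| Grade 2, intolerable; Grade 3 or 4 | Withhold until Grade 1 or lower | Interrupt until Grade 1 or lower | Consistent |

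The conflict is confined to the middle line.

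**Step 2. Before diagnosis.** Section 8.2.1.5 interrupts at any Grade 2 or higher ocular event until the evaluation is done. Interrupting, evaluating and then applying the Section 8.5 row is a workable order. The difficulty begins when the evaluation confirms serous retinopathy, because Section 8.5 then gives two answers.

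**Step 3. CTCAE version.** The row names v4; Section 15.1, the synopsis and Section 17.2.2 name v5.0. The note under the renal table in Section 8.4.2.10, which says those guidelines apply under both v4.0 and v5.0, belongs to that table and does not cover the ocular rows. The documents reproduce neither scale, so whether an event would be graded differently cannot be determined from them.

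**Step 4. Number of patients.** Inputs:

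- Maximum cobimetinib patients: 33 (Section 24.3.1).
- Single-agent study: serous retinopathy in 2.6%, all Grade 1 or 2, with eye examinations for patients reporting visual disturbance (Section 8.2.1.5).
- Phase III vemurafenib combination: serous retinopathy in 24% with serial examinations, about 50% asymptomatic Grade 1; Grade 3 ocular events in 2.8% (Section 8.2.1.5).

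Single-agent source: 33 × 0.026 = 0.86. This is an upper bound, because the 2.6% includes Grade 1.

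Combination source: Grade 2 or higher is 0.24 × (1 − 0.50) = 0.12, and 33 × 0.12 = 3.96. If all of the 2.8% were serous retinopathy, Grade 2 alone would be 0.12 − 0.028 = 0.092, and 33 × 0.092 = 3.04. The tolerable share is not given and could be anything from none to all, so this source supports a range of 0 to about 4.

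The combination calculation applies a share that may count events to a rate that counts patients, so it is approximate. The dosing table in Section 7.4 shows 40 patients for this arm instead of 33. With 40, the two upper bounds become 40 × 0.026 = 1.04 and 40 × 0.12 = 4.8, which does not change the conclusion.

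**The case against.** The best defence is that the withhold line sits in a narrative cell headed as general guidance, is worded as a recommendation, and is followed by a list of management options. The row below is specific to grade and tolerability, and many sites would act on it. This makes divergent practice a possibility and not a demonstrated fact. It does not remove the conflict. No precedence is stated, and the row for intolerable Grade 2 or Grade 3/4 repeats the general guidance's own action, so both lines are directing the same decision.

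There are also safeguards. The table sends visual complaints to an ophthalmologist, Section 6 schedules serial examinations, and Section 8.6 lets the investigator reduce the dose for toxicity of any grade. These limit the risk to patients, but none says which line is the default. Section 8.6 also asks for advance approval of any modification of the dose guidelines.

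Three stronger readings are tempting, and the documents do not support them:

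- **That Section 8.2.1.5 is a third contradictory rule.** It applies while evaluation is pending, so it can precede either Section 8.5 instruction without contradiction.
- **That the v4 label makes the dosing grade differ from the recorded grade.** Neither scale is reproduced, so no difference is shown. The label may be left over from the change to v5.0 listed in the revision record, but that is an inference.
- **That serous retinopathy is by name an immediately reportable event of special interest.** The cobimetinib list in Section 16.2 is damaged in the available text and the term cannot be read there, so the point does not rely on it.

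**Conclusion.** The concern holds in a limited form. For diagnosed, tolerable Grade 2 serous retinopathy, two adjacent lines of the Section 8.5 ocular table give incompatible cobimetinib instructions, and nothing in the protocol ranks them. This is an internal inconsistency, and it follows from the wording alone, whatever the number of cases.

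The number is likely to be small: under 1 patient at the single-agent rate and 0 to about 4 on the combination figures, out of at most 33. A reader might take the 3.04 in the calculation as an expected count of affected patients. It is not: it counts all Grade 2 events, whether tolerable or not, assumes that every Grade 3 ocular event was serous retinopathy, and carries a rate over from a different drug combination. Transfer of either source to cobimetinib with atezolizumab is an assumption. The single-agent study examined patients who reported visual disturbance, whereas this trial examines on a schedule, as the combination study did.

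The CTCAE version mismatch is real but editorial on the present evidence. The point should be corrected because the instructions concern a known retinal toxicity and the correction is inexpensive. Which instruction is clinically right is for the sponsor to decide, and no view is offered here.

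**What to change.** The sponsor should reconcile the Section 8.5 ocular general guidance, the Section 8.5 serous retinopathy rows and the interruption sentence in Section 8.2.1.5, so that tolerable Grade 2 has one stated instruction on cobimetinib while evaluation is pending and one after diagnosis. If the split between tolerable and intolerable stays, the protocol should say how it is judged.

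The row label should be changed to CTCAE v5.0, or a note should state that the row applies under both versions, as the note to the renal table in Section 8.4.2.10 already does.

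The cost is wording in a few places and no added examinations or visits. Because dosing instructions are not administrative text, Section 22.2 calls for ethics committee approval of the amendment. It can be combined with the next planned one, provided that sites receive a single clarification in the meantime through the routes the protocol allows.
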